#### 10.2.2. Serious adverse event or serious adverse reaction

A serious adverse event (SAE) or a serious adverse reaction (SAR) is an AE or AR occurring during the study phase that fulfils one or more of the following criteria:

- Results in death
- Is life-threatening (NOTE: the term “life threatening” in the definition of serious refers to an event/reaction in which the subject is at risk of death at the time of the event/reaction; it does not refer to an event/reaction which hypothetically might have caused death if it were more severe)
- Requires inpatient hospitalization or prolongation of existing hospitalization (planned hospitalization is not to be reported as SAE or SAR)
- Results in persistent or significant disability/incapacity
- Is a congenital anomaly/birth defect despite birth control during the study

All SAEs and SARs will be registered and reported to the sponsor by primary investigator as described below.

A SAR is unexpected (i.e. suspected unexpected serious adverse reaction, SUSAR) if it is not consistent with the description in the medicinal product source document. The Research Ethics Committee and Danish Medicines Agency will annually be presented with a list of all SAR and SUSAR that have occurred during the trial as well as an evaluation of patient safety until the trial has concluded. All fatal or life threatening SUSARs are reported to the Danish Health and Medicines Authority and The Research Ethics Committee as soon as possible and no later than 7 days after the sponsor has been notified of SUSAR.

Investigator must report any SAE, SAR, or SUSAR to the sponsor immediately (within 24 hours) in order for sponsor to report to the Danish Healthy and Medicines Authority in time. As patients with AP often experience serious complications during admission as part of the disease, the list below entails SAEs that will not be reported to sponsor immediately (non-immediate reporting). These will instead be reported to sponsor within no more than 7 days:

- Sepsis or septic shock
- Kidney failure
- ARDS (acute respiratory distress syndrome)

Within 7 days after reporting of SUSAR, the sponsor must notify the Danish Health and Medicines Authority about all relevant information of the sponsor and investigator's follow-up on the SUSAR. All other SUSARs

should be reported to the Danish Health and Medicines Authority within 15 days after the sponsor has been notified of the SUSAR. SUSAR's will be unblinded prior to any report to authorities.

All SUSARs will be reported electronic to the Danish Health and Medicines Authority using the following e-form on their home page: "Reporting of suspected unexpected serious adverse reactions (SUSARs) seen in clinical trials". Additionally, all SUSARs must immediately be notified to The Research Ethics Committee. Any report must be accompanied with comments regarding possible consequences for the trial. The assessment of SUSAR will be made before unblinding.

#### 10.2.3. Safety follow-up procedure

All SAE's and related AE's must be followed-up until the event has resolved or stabilized, or the relationship to study medication is clarified. All participants with unresolved events at the end of the study, except those who dropped out before randomization or starting active treatment, must be included in a safety follow-up visit in order to check response of events to de-challenge. The safety follow-up visit should take place one to two weeks after the Final Examination / Premature Termination. Events, which are not complete in this way by the end of the period of observation, must be followed-up on until this status has been achieved. Follow-up can be waivered in specific cases after consultation with sponsor. This permission must be documented per case and retained in the investigator site file and trial master file.

#### 10.3. Quality control and quality assurance

Quality Control is defined as the operational techniques and activities undertaken within the quality assurance system to verify that the requirements for quality of the study related activities have been fulfilled. Quality Control will be applied to each stage of data handling to ensure that all data are reliable and have been processed correctly, according to standard CGP-guidelines.

Quality Assurance is defined as the planned and systematic actions that are established to ensure that the study is performed, and the data are generated, documented (recorded), and reported in compliance with GCP and the applicable regulatory requirements. An independent audit at the study site may take place at any time during or after the study. The study will be monitored by an independent company/person not otherwise involved in the project. Furthermore, monitoring visits to the trial site will be made periodically during the trial to ensure that all aspects of the protocol are followed. Source documents will be reviewed for verification of agreement with data on CRFs. The Investigator/institution guarantees direct access to source documents to appropriate regulatory agencies. The trial site may also be audited (quality assurance) or inspected by appropriate regulatory agencies. It is important that the investigator and their relevant

personnel are available during the monitoring visits and possible audits and that enough time is devoted to the process.

## 11. Ethics and dissemination

This clinical study will be conducted in compliance with Good Clinical Practice (CPMP/ICH/135/95), designated Standard Operating Procedures, the Danish Medicines Agency, the North Denmark Region Committee on Health Research Ethics, and within the principles of the Declaration of Helsinki (amended by the 64th WMA General Assembly, Fortaleza, Brazil, October 2013). Additionally, this study will be undertaken in accordance with the Protocol and Good Clinical Practice on the conducting and monitoring of clinical studies. The trial will only be initiated once the approvals from the North Denmark Region Committee on Health Research Ethics and the Danish Medicines Agency are given. Any significant modifications to the protocol, will be submitted as protocol amendments and subsequently approved by the North Denmark Region Committee on Health Research Ethics and the Danish Medicines Agency before implementation.

### 11.1. Risks related to the experimental procedures

Biochemical tests including blood samples, PEG 400/4000 test, bear little risk for the patients and furthermore are all part of the standard evaluation of these diseases.

CT-scans involve radiation and careful consideration should always be applied when using this modality in clinical research. Patients admitted with AP will have CT-scans performed upon admission and at 5 day follow up (+/- 1 day). In Denmark, the estimated average radiation dose from one CT-scan of the abdomen is 11,9 millisievert (mSV) (33). Thus, the modality bears significant risk for individuals participating in the study. It is part of the standard diagnosis strategy to perform a CT-scan on patients admitted with symptoms of AP and many patients will have a follow up CT-scan prior to discharge to evaluate the presence of complications including pancreatic necrosis and fluid collections. The CT-scans will also be available for the attending physicians. Furthermore, we expect the utility of the data collected to potentially promote prevention and better treatment of AP, which is a severe medical condition. Hence, we find it ethically sound to perform the study as described.

### 11.2. Risks related to study medication

Treatment with PAMORA may be uncomfortable for patients as they may experience side effects like diarrhea or nausea. PAMORAs, especially methylnaltrexone, can worsen the clinical course of intestinal stenosis, because they increase motility and secretion in the intestine. At worst, this can cause perforation of the intestines which can be fatal. This has been accounted for in the exclusion criteria (see section 7.2.2.).

Participation in the study will be potentially beneficial for patients with AP receiving active medication and it is expected that this study will produce important knowledge on the treatment of AP for future patients. In

this regard, the use of placebo is crucial for evaluating the true effect of PAMORAs on the course of disease. Furthermore, all patients, regardless of whether they receive active treatment or placebo, may gain new insights and understanding into the pathophysiology of their disease and possible beneficial future treatment. The treatment of patients receiving placebo will not be affected by participation in the study as they still receive standard treatment.

In conclusion, the risk the participants are exposed to in this study is minimal compared to the beneficial information that will be gained from the study – both for the individual patient, but also for future treatment of patients with AP.

### 11.3. Patient insurance

Clinical responsibility befalls the University Hospitals involved in the study. All participants will be covered by the patient insurance of the respective site of trial conduction. Participation in a trial involving medical treatment may alter private insurance status, should the participant wish to travel during or right after study participation. Participants are advised to seek consultancy from their insurance agency if they plan to travel during or right after participation in the study.

### 11.4. Consent and confidentiality

The informed consent will be obtained following oral and written information has been given by competent delegated study personnel as previously described in section 7.8. Once informed consent is signed, this allows investigators; monitors from The Good Clinical Practice Unit at Aalborg and Aarhus University Hospitals; GCP inspection; and Danish Health as well as Medical Authority to assess patients' medical records with the purpose of retrieving information necessary for study conduction, monitoring and inspection. Detailed clinical characterization of the patient, complementary information in relation to the study will be made available from medical records so that sponsor and monitor can control the quality of the study regarding "informationsbekendtgørelsen". Information about participants is protected by "databeskyttelsesforordningen", "databeskyttelsesloven", and "sundhedsloven".

### 11.5. Declaration of interests

None.

### 11.6. Access to data

The trial will be registered at clinicaltrialregister.eu and EudraCT, and at the end of the study, the results will also be published at these websites. All results will be published as open access whenever possible using both

scientific and public media. When the clinical trial ends, the anonymized data will be made available to other researchers through relevant and actual public databases such as Zenodo.

### [11.7. Dissemination policy](#)

Results, positive as well as negative and inconclusive, will be released to the public, and may be published in peer-reviewed scientific journals. Results may also be used in submission to regulatory authorities. The first author will be appointed according to the Vancouver system. The investigator will inform the Danish Medicines Agency and the Research Ethics Committee after the termination of the trial. No later than 90 days after trial termination, the “Declaration of the end of trial form” must be submitted to The Danish Medicines Agency, and as soon as possible or within 1 year the results will be registered with EudraCT. The Research Ethics Committee will be notified of results from this study. Published articles are sent to The Danish Medicines Agency and the Research Ethics Committee.

For patients with acute pancreatitis, pain is the dominant symptom and thus they are exposed to increased amounts of both endo- and exogenous opioids. Opioid administration is known to cause opioid-induced bowel dysfunction primarily by binding μ -opioid receptors in the enteric nervous system (3,4). Thus, opioids promote dysmotility and prolonged gut transit time, which together can cause small intestinal bacterial overgrowth (4). Furthermore, opioids may increase intestinal permeability, resulting in the translocation of bacteria from the gut to the peripancreatic tissue and systemic circulation. Potentially, translocation of bacteria may lead to local and systemic infections, which further may be facilitated by opioid-induced immunosuppression (5,6). Opioids also affect the pancreas directly by decreasing fluid secretion in the pancreatic duct system and increasing the frequency of contractions in the sphincter of Oddi (4,7). This may lead to decreased wash-out of intrapancreatic activated enzymes and thus worsen autodigestion of the tissue and subsequent inflammation of the pancreas. Peripherally acting μ -opioid receptor antagonists (PAMORAs) bind to the μ -opioid receptor with an affinity much stronger than opioid analgesics and thus have the potential to counteract harmful effects of opioids despite high levels of exogenous opioids in patients with pancreatitis.

We hypothesize that treatment with the PAMORA methylnaltrexone will reduce disease severity in patients with acute pancreatitis, compared to placebo. We plan to test this hypothesis by treating patients admitted with acute pancreatitis with methylnaltrexone or placebo in a 1:1 randomization design.

2. Study Objectives, Hypothesis and Outcomes

2.1. Primary Objective and Outcome

The primary objective is to evaluate disease severity in patients with acute pancreatitis during treatment with methylnaltrexone or placebo. The primary outcome will be assessed using the Pancreatitis Activity Scoring System (PASS) score.

PASS is a validated assessment tool for acute pancreatitis based on 5 clinical parameters, which are weighed according to figure 1 (8). It quantitatively evaluates the disease course of acute pancreatitis and has proven useful for monitoring disease severity as well as predicting clinical outcome in patients admitted with this disease (9). Organ failure (i.e. renal, respiratory and cardiovascular) will be assessed according to the Modified Marshall scoring system as defined in the Revised Atlanta criteria (10). Thus, organ failure of the cardiovascular and renal system, is assessed by means of systolic blood pressure and serum creatinine respectively. The ratio between partial pressure of oxygen in arterial blood (PaO_2) and the fraction of inspired oxygen (FiO_2) is used to assess the respiratory system. Not all participants included into this study are expected to have PaO_2 values available. Thus, we will use the ratio between peripheral capillary oxygen saturation (SpO_2) and FiO_2 instead, as previous studies have shown that these two ratios correlate well (11,12).

Pancreatitis activity scoring system

Clinical feature	Weight
Organ failure	100 per system
Intolerance to solid diet	0/40 (N/Y)
Systemic inflammatory response syndrome (SIRS)	25 per criteria
Abdominal pain	(0-10) x 5
Intravenous morphine equivalent dose (mg)	(1/mg) x 5

EXAMPLE: Patient with acute pancreatitis

Kidney failure, tolerant to solid diet, fulfills 1 SIRS criteria, scores abdominal pain 6, need of 20 mg intravenous morphine
 $PASS = 100 + 0 + 25 + (6*5) + (20*5) = 255$

SIRS criteria
1. Body temperature $> 38^{\circ}\text{C}$ or $< 36^{\circ}\text{C}$
2. Heart rate $> 90/\text{min}$
3. Respiration $> 20/\text{min}$ or $\text{PaCO}_2 < 32\text{mmHg}$
4. White blood cell count $> 12.0 \times 10^9/\text{L}$ or $< 4.0 \times 10^9/\text{L}$

EXAMPLE: Patient with acute pancreatitis

Body temperature 37.8°C , Heart rate 120, Respiration 19/min
White blood cell count $18.0 \times 10^9/\text{L}$
 $SIRS score = 0 + 1 + 0 + 1 = 2$

Figure 1

We hypothesize that treatment with the PAMORA methylnaltrexone will reduce disease severity as measured by a lower PASS-scores, compared to placebo.

2.2. Secondary Objectives and Outcomes

The secondary objective is to document the effects of methylnaltrexone treatment on several clinical outcomes in patients with acute pancreatitis.

The secondary outcomes are listed below:

- Difference between treatment groups (methylnaltrexone or placebo) in daily PASS-scores during treatment and at 14-day follow-up
- Difference between treatment groups on disease severity assessed using the revised Atlanta criteria (10), where patients are put into one of three categories (mild/moderate/severe)
- Difference between treatment groups on subjective measures of pain intensity and gastrointestinal function assessed using validated questionnaires (13–15) daily during treatment and at 14-day follow-up
- Difference between treatment groups in length of admission and mortality, assessed retrospectively 90 days after admission, using the patients' medical records

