### 7.3. Interventions

#### 7.3.1. Methylnaltrexone dosage and treatment duration

To ensure standardization of the protocol, patients with AP will be treated with methylnaltrexone or placebo intravenously for the first 5 days of admission and assessments of endpoints will be done at fixed time points during this period. The dosage will be weight adjusted. Thus, 0.15 mg/kg methylnaltrexone or a corresponding volume of matching placebo (Ringer's lactate) will be dissolved in 1000 mL Ringer's lactate solution and given as a continues infusion over 24 hours using an infusion pump. In accordance with the summary of product characteristics for methylnaltrexone, a 50 % dose reduction will be made for patients with an eGFR below 30 ml/min/1,73m^2. the continuous infusion of study medication will be started no later than 24 hours after preparation. This will be ensured by keeping detailed record on the time of preparation

as well as time of infusion start. As methylnaltrexone is sensitive to light, the solution will be kept protected from light from the time of preparation until the time of infusion start. Two persons trained in the protocol and delegated to do so, will prepare the solution of study medication together. This will be done with one person assisting virtually in exceptional cases.

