### 7.4.2. Secondary endpoints

- Difference in daily **PASS scores** between subgroups
- Difference in daily assessments of circulating **pro- and anti-inflammatory markers** (including CRP, IL-6, IL-8, IL-18, TNF- $\alpha$  and CD163) as well as **intestinal barrier markers** between subgroups
- Difference in **intestinal permeability** between subgroups measured from 48 to 72 hours after randomization using the oral polyethylene glycol 400/4000 test
- Difference in **intestinal motility** assessed by means of gut/colon transit using a CT-based radiopaque marker method on day 5 (+/- 1 day) between subgroups
- Difference in **pancreatic complications** (e.g. edema, fluid collections and necrosis) assessed and quantified with contrast-enhanced CT on day 5 (+/- 1 day) after randomization (20)
- Difference between subgroups in the following **clinical outcome parameters**: pain intensity and gut function (assessed by questionnaires), quantification of analgesics (separated into opioids and non-opioids), need for nutritional support, disease severity, invasive treatments, intensive care and hospital stay, as well as mortality during total hospitalization
- Difference in **health resource utilization** during hospitalization between subgroups

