#### 7.7. Recruitment

Patients admitted with AP will be identified and contacted by study personnel upon or during admission. Information regarding current and previous medical conditions will be passed on by the treatment-responsible physician from medical records to study personnel in order to identify eligible patients. This will be ensured by study personnel being in daily contact with the staff at the relevant departments at the respective inclusion sites with the purpose of monitoring the development of SIRS in patients with AP. This will be conducted in accordance to "Sundhedsloven § 46, stk. 1", under the responsibility of the primary investigator at the respective centers. AP is a relatively common disease and thus we expect approximately 10 patients to be admitted in total every week at our four inclusions sites. We expect at least half of these (i.e. 5) to be eligible for participation in the study.

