#### 9.1.2. Clinical outcome and health resource utilization

Clinical outcomes and health resource utilization are documented using preformed questionnaires and by means of the medical records. Thus, participants will be asked to fill out three questionnaires daily: i) The modified Brief Pain Inventory short form, ii) Bristol Stool Form Scale and iii) Gastrointestinal Symptom Rating Scale (GSRS). For a detailed description of these, see below. From the patients' medical records, the following will be registered: i) presence of local and systemic complications as well as organ failure (transient or persistent), used to classify the severity of AP according to the revised Atlanta criteria (20), ii) need for intensive care unit admission, iii) need for analgesics, iv) nutritional support, v) invasive treatment, vi) duration of hospitalization, and vii) mortality. Total duration of hospitalization, readmission rates and mortality will be determined retrospectively 30 and 90 days after admission using the patients' medical records.

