- Pre-existing renal insufficiency (defined as habitual estimated glomerular filtration rate (eGFR) below 45 ml/min/1,73m²)
- End-stage renal impairment requiring dialysis prior to inclusion
- Severe pre-existing comorbidities (assessed by investigator upon inclusion)
- Severe non-pancreaticobiliary infections or sepsis caused by non-pancreaticobiliary disease
- Child-Pugh class B or C liver cirrhosis
- Lactating

5. Data handling

Outcome	Source	Data collection rate	Datatype
PASS-score	From the patients' medical records (vital signs, lab results, quantification of need for opioid treatment), self-reported pain intensity and self-reported tolerance to solid foods	Daily during treatment and at 14-day follow-up	Ratio
Disease severity	Stratified as mild/moderate/severe using information about complications and organ failure from medical files	At 14-day follow-up	Ordinal
Subjective measures of pain intensity	Questionnaire: Pain intensity (current + worst/least pain the past 24 hours using NRS), pain interference score (7 parameters, scores 0-10)	Daily during treatment and at 14-day follow-up	Ordinal
Length of admission	Medical records, no. of days	90 days after randomization	Ratio
Mortality	Medical records; deceased y/n	90 days after randomization	Nominal
Circulating levels of pro- and anti-inflammatory cytokines,	Blood samples	Daily during treatment and at 14-day follow-up	Ratio
Intestinal permeability, gut transit time	Urine samples, CT-scans	Once during treatment (day 2-3)	Ratio
Prevalence of pancreatic complications	Stratified according to the revised Atlanta criteria (21) based on CT-scan	On day 5	Ordinal

Table 1

Delegated trial personnel at each trial center will register the collected data in the electronic case report form (eCRF) using the electronic data capture tool REDCap (Research Electronic Data Capture, version 10.6.26) hosted by the organization of The North Denmark Region. REDCap is a secure browser-based software, which meets all regulatory safety requirements (22,23). Data recording will begin when a participant is included and will occur gradually to the end of the trial. A detailed record of any corrections will be kept within REDCap. REDCap also contains features to improve data validation in the form of predefined variable ranges, options to detect that dates are in correct order and warnings if the forms are not sufficiently filled in.

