6.2. Secondary and exploratory analyses

Secondary and exploratory outcomes will be presented graphically to illustrate trends and potential differences between groups. Thus, outcomes measured repeatedly (PASS-score and levels of pro- and anti-inflammatory cytokines) will be illustrated using trend curves for each treatment group with single time points represented as mean and standard deviation or median and interquartile range, depending on normality. Single time point outcomes will be presented using boxplots depicting the difference between mean and standard deviation or median and interquartile range, depending on normality. Statistical analysis will also be performed for these outcomes according to below.

Repeated measures (e.g. daily PASS-scores, levels of pro- and anti-inflammatory cytokines, subjective measures of pain intensity)

For analysis of repeatedly measured secondary outcomes (daily PASS-scores, daily levels of pro- and anti-inflammatory cytokines), a repeated measures linear mixed-effects model will be used, as described for the primary endpoint. Furthermore, summary statistics and trend curves of PASS scores will be provided for the individual time points.

Single time point outcomes (length of admission, intestinal permeability and gut transit time)

Single time point outcomes (length of admission, measures of gut permeability and transit time) will be compared between groups using the two-sample unpaired t-test, when normality can be confirmed using the Shapiro-Wilk test, or the non-parametric analysis Mann-Whitney U-test when normality cannot be confirmed.

Counted data (disease severity, mortality)

After each patient has been placed in one of three categories (mild/moderate/severe), we will assess whether the prevalence of ‘moderate-to-severe’ disease is different between the two treatment groups. Thus, a 2 x 2 contingency table will be calculated (‘experienced event’ (D) being moderate or severe disease, ‘did not experience event’ (H) being mild disease and the χ^2 test will be employed to test the null hypothesis of no difference between groups.

Mortality between groups (assessed 90 days after randomization) will be analyzed using a 2 x 2 contingency table (‘experienced event’ (D) being death, ‘did not experience event’ (H) being survival). As we expect few of our patients to die during the study period, we plan to use Fishers exact test to test the null hypothesis of no difference between groups.

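### The 90-day mortality window starts at admission in some sections and at randomization in others, and length of stay counts hospital days spent before randomization

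*SAP*

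**What the plan says.** **The 90-day clock.** SAP 2.2 has "length of admission and mortality, assessed retrospectively 90 days after admission". Protocol 9.1.2 agrees on the origin and adds a 30-day review: "Total duration of hospitalization, readmission rates and mortality will be determined retrospectively 30 and 90 days after admission". SAP Table 1 (section 5, Data handling) gives "90 days after randomization" for both length of admission and mortality, and SAP 6.2 has "Mortality between groups (assessed 90 days after randomization". The endpoint list in Protocol 7.4.2 has a further version, "mortality during total hospitalization".

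**Length of stay.** The SAP measures length of admission as a number of days from the medical records, and the protocol measures total hospitalization. SAP 6.2 compares it between arms by t-test or Mann-Whitney test, without adjustment. No section starts the count at randomization.

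**Time of entry.** Protocol 7.2.1 requires the diagnosis during the current admission and the SIRS criteria in the 24 hours before inclusion. It sets no maximum time since admission. Under Protocol 7.7 patients "will be identified and contacted by study personnel upon or during admission", and staff follow the wards daily for SIRS that develops. Two sections point to early entry: Protocol 7.3.1 describes treatment given "intravenously for the first 5 days of admission", and SAP 4.1 has patients contacted on admission. SAP 2.4 lists symptom onset to admission and symptom onset to randomization as separate descriptive variables, so the SAP recognises that there may be a gap.

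**The concern.** Two issues share one cause: admission and randomization are treated as interchangeable starting points.

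First, a death that falls between 90 days after admission and 90 days after randomization counts under SAP Table 1 and 6.2 but not under SAP 2.2 or Protocol 9.1.2. A late in-hospital death could count only under Protocol 7.4.2. The analyst would have to choose, and the plan should make that choice in advance.

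Second, hospital days before randomization are fixed before allocation. Including them in length of stay adds variation that treatment cannot influence, and so costs precision on a secondary outcome in a trial of 45 per arm.

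**Working it through.** **1. The plan's own figure.** The only sample size given is for PASS (Protocol 7.6, SAP 3.1): difference 25, SD 40, 80% power, two-sided 0.05.

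n per group = 2 × (1.960 + 0.842)² × (40/25)² = 2 × 7.851 × 2.56 = 40.2, rounded up to 41.

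This reproduces the stated 41. It concerns PASS at 48 hours after randomization, so nothing below alters it. No figure is given for length of stay or mortality.

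**2. The clocks side by side.**

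| Place | Mortality window | Length of stay |
|---|---|---|
| SAP 2.2 | 90 days from admission | reviewed 90 days from admission |
| Protocol 9.1.2 | 30 and 90 days from admission | total stay, same review dates |
| SAP Table 1 | 90 days from randomization | number of days, reviewed 90 days from randomization |
| SAP 6.2 | 90 days from randomization | no window or origin given |
| Protocol 7.4.2 | while in hospital | hospital stay |

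The two 90-day clocks agree only if every patient is randomized on the day of admission. For length of stay, the 90-day entry is a look-up date and does not set the start of the day count.

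**3. Follow-up under the admission clock.** Follow-up after randomization = 90 − delay. For assumed delays of 1, 3, 7 and 10 days this gives 89, 87, 83 and 80 days. Under the randomization clock every patient has 90.

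**4. Effect on mortality.** Protocol 6.1 puts mortality near 3%, so 90 × 0.03 = 2.7 deaths are expected. Assume a constant hazard h = −ln(0.97)/90 per day. If every patient had the same delay, the deaths moved across the cut-off would be 90 × [exp(−h(90 − delay)) − exp(−90h)]. This is 0.03 for a delay of 1 day and 0.21 for 7 days.

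**5. Effect on length of stay.** Let s be the SD of stay after randomization and d the SD of the delay, assumed independent. Neither is in the documents, so these are illustrative ranges. Variance inflation = (s² + d²)/s², and the equivalent number of patients is 90 divided by the inflation.

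| s (days) | d (days) | Inflation | Equivalent N of 90 |
|---|---|---|---|
| 5 | 1 | 1.04 | 87 |
| 5 | 2 | 1.16 | 78 |
| 5 | 3 | 1.36 | 66 |
| 8 | 1 | 1.016 | 89 |
| 8 | 2 | 1.062 | 85 |
| 8 | 3 | 1.141 | 79 |

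Over a wider grid (s from 4 to 10, d from 0.5 to 3) the variance rises by 0.3% to 56%. At 41 per group, for an effect of 0.625 s, power is 80.8% without the delay. It falls to 77.7% in a middle case (s = 7, d = 2) and to 61.9% in the worst case (s = 4, d = 3).

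**6. Chance imbalance in delay.** With 45 per arm, the SE of the difference in mean delay is d × √(2/45) = 0.21, 0.42 or 0.63 days for d = 1, 2 or 3. A 1-day imbalance would be 4.7, 2.4 or 1.6 SE.

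**The case against.** The strongest reply is that this is largely harmless. SAP 6.2, the section that will govern the mortality analysis, already uses randomization. Few deaths are expected. Protocol 7.3.1 and SAP 4.1 suggest that patients enter soon after admission, and the interval can be derived from SAP 2.4. Total stay is a legitimate outcome and fits the resource-use endpoint. The variance figures rest on assumed SDs and independence. They apply to a t-test and do not carry over directly to the Mann-Whitney test that SAP 6.2 uses if normality fails. Secondary endpoints are analysed per protocol, so the base may be below 90.

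Most of this stands, and it limits the size of the point. It does not remove the contradiction between the sections. Nor does it impose a limit on delay, since neither early-entry statement is an eligibility criterion.

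Four stronger readings are tempting, and the documents do not support them:

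- *The stay comparison is biased.* Delay is fixed before allocation and balanced in expectation between the randomized arms. Uneven per-protocol exclusions, which SAP 2.5 itself anticipates, are a separate matter and would affect stay from either origin. Nothing in the documents ties them to delay.
- *Chance imbalance in delay is a further harm.* It is already in the standard error, so it is the same cost as the variance inflation. A full day's imbalance is unlikely unless the delay varies widely (step 6).
- *The arms have unequal follow-up.* Under the admission clock follow-up differs between patients, not systematically between arms.
- *Late entry is common.* It is permitted, but no distribution of delay is given.

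**Conclusion.** The conflicting 90-day clocks are wrong as written: the SAP disagrees with itself, and the protocol adds an in-hospital version. Counting stay from admission is not an error, and changing its origin is a cheap improvement in precision.

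Overall severity is minor. The gain for length of stay could be trivial or moderate, depending on a spread of delay that only the trial data can show. For mortality the issue is definition, since the expected shift is a fraction of one death for delays of up to a week under a constant hazard. The primary endpoint, timed from randomization, is unaffected.

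**What to change.** Before the data are analysed:

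1. In SAP 2.2, Table 1 and 6.2 and in Protocol 9.1.2, make 90 days after randomization the single mortality window, and time the protocol's 30- and 90-day reviews, including readmission, the same way. Align the mortality entry in Protocol 7.4.2.
2. In the same sections, define the tested length of stay as days from randomization to discharge. Keep total admission length as a descriptive resource-use figure.
3. Report the admission-to-randomization interval by arm, as the difference between the two times already listed in SAP 2.4.
4. Reconcile Protocol 7.3.1 and SAP 4.1, which imply entry at admission, with Protocol 7.2.1 and 7.7, which allow it later.

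The cost is wording in the two documents, plus taking discharge and death dates from the medical records, because SAP Table 1 lists only a number of days and a yes/no for death. The one loss is that whole-admission stay is described and no longer tested.
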